## 1. Version History

Version	Revision Date	Summary of Changes	Author(s)/Title
A	24MAY2017	New Document	[REDACTED]
B	18JUL2017	
 
Added Matlab software to list of software than can be used for analysis
 
Bootstrap of Arms, Mean Bias and Standard Deviation removed as not intended for study endpoint acceptance criterion
 
Revise requirements for Bland-Altman and Linear Regression graphs
 
Updates to subgroup analysis requirements
 
Lin's CCC does not have regression coefficients as this is not regression model but only correlation statistic
 
Sample Size justification statement justification
 
	[REDACTED]

This document is electronically controlled. Printed copies are considered uncontrolled.

Confidential MDT16010MAVJB3	[REDACTED]	[REDACTED]
--------------------------------	------------	------------

## 2. List of Abbreviations and Definitions of Terms

Abbreviation	Definition
ARMS	Arithmetic Root Mean Square
CIP	Clinical Investigation Plan
etCO 2	End Tidal Carbon Dioxide
fSO 2	Global Field Saturation
NIRS	Near Infrared Spectroscopy
OPC	Objective Criterion
rSO 2	Regional Saturation Measured by NIRS System
SAP	Statistical Analysis Plan
SaO 2	Saturation of Arterial Blood
SjvO 2	Jugular Bulb Venous Saturation
SpO 2	Arterial Blood Oxygen Saturation
StO 2	Absolute Levels of Blood Oxygenation Saturation in the Tissue
UCB	Upper Confidence Bound

## 3. Introduction

This document describes the statistical analyses and data presentations to be performed for Medtronic Study Protocol, MDT16010MAVJB3, "Validation of Next Generation INVOS NIRS Cerebral and Tissue Oximeter to Measure Cerebral and Somatic Tissue Oxygen Saturation in Healthy Volunteers". This statistical analysis plan (SAP) provides a comprehensive and detailed description of the strategy, rationale, and statistical techniques to be used to validate the [REDACTED] System (investigational preamplifiers, monitor, and associated cables) in conjunction with Adult sensor [REDACTED].

All statistical analyses detailed in this SAP will be conducted using SAS® Version 9.3 or higher, JMP Version 11.2.0, Minitab Version 17.1.0, Matlab Version 2015a or higher, or other validated software.

This document is electronically controlled. Printed copies are considered uncontrolled.

Confidential MDT16010MAVJB3	[REDACTED]	[REDACTED]
---------------------------------------	------------	------------

[figure not shown]
## 4. Study Objectives

The primary objective of the study is to validate that the [REDACTED] System in conjunction with Adult Sensors [REDACTED] meet product requirements for cerebral accuracy, cerebral trending accuracy, and somatic trending.

## 5. Investigation Plan

This is a prospective data collection, non-randomized, single center study to validate an investigational Next Generation INVOS system. An investigational next generation INVOS Near Infrared Spectroscopy (NIRS) system includes production equivalent [REDACTED] System (investigational preamplifiers, monitor, and associated cables) in conjunction with Adult sensor [REDACTED] (INVOS system).

This study will be conducted in three phases: Enrollment Phase, Desaturation Phase, and Follow-up Phase. During enrollment phase, subjects will be screened and qualified subjects will be enrolled. After enrollment, during desaturation phase, two investigational INVOS sensors are placed on the patient's forehead and other sensors may be placed on somatic sites. The Next Generation INVOS system will be evaluated for a targeted range of 70-100% arterial blood oxygen saturation (SpO2) levels that are measured by a pulse oximeter. Hypoxic mixtures of gas are delivered and INVOS and SpO2 data are collected at approximately 5-minute intervals during periods of ascending and descending concentration of control of blood carbon dioxide and oxygen levels. At each plateau, blood samples are drawn simultaneously from both jugular bulb and the radial arterial catheters and analyzed for hemoglobin oxygen saturation levels using a co-oximeter.

- 2 sensors on cerebral site (left, right side of forehead)
- 2 blood draws and monitor measurements at each oxygenation plateau
- 1st data point at beginning of each sequence for trending accuracy used for baseline reference
- Somatic Trending Accuracy data is collected for all Sequences #1-3. [REDACTED] does not have an effect on somatic blood oxygenation levels.

This document is electronically controlled. Printed copies are considered uncontrolled.

Confidential MDT16010MAVJB3	[REDACTED]	[REDACTED]
---------------------------------------	------------	------------

During the invasive breathe-down protocol, a subject breathes varying levels of oxygen (desaturation sequence) while paired venous and arterial blood draws are collected. [REDACTED]

[REDACTED] Based on the measured oxygenation content of each blood sample, a calculated estimate of  $\text{SO}_2$  ( $\text{fSO}_2$ ) is created for each paired blood draw. The calculated  $\text{fSO}_2$  (blood reference) is compared to the average  $\text{rSO}_2$  from each INVOS sensor during the time span of collection for the paired blood draw [REDACTED]. [REDACTED]

## 6. Determination of Sample Size

Cerebral Overall Accuracy:

Based on data from similar studies, a mean value of [REDACTED] is assumed for  $A_{\text{RMS}}$  with a standard deviation of [REDACTED] assumed. A total of 25 subjects will provide sufficient data information [Table 2] to assess the statistical hypothesis. [REDACTED] power and an alpha of [REDACTED] are assumed in the estimation.

Cerebral Trending:

Based on data from similar studies, a mean value of [REDACTED] is assumed for  $A_{\text{RMS}}$  with a standard deviation of [REDACTED] assumed. A total of 25 subjects will provide sufficient data information [Table 2] to assess the statistical hypothesis. [REDACTED] power and an alpha of [REDACTED] are assumed in the estimation.

Somatic Trending:

Based on data from similar studies, a mean value of [REDACTED] is assumed for  $A_{\text{RMS}}$  with a standard deviation of [REDACTED] assumed. A total of 25 subjects will provide sufficient data information [Table 2] to assess the statistical hypothesis. [REDACTED] power and an alpha of [REDACTED] are assumed in the estimation.

This document is electronically controlled. Printed copies are considered uncontrolled.

Confidential MDT16010MAVJB3	RE00083415	Rev B 18JUL2017 RC100021
---------------------------------------	------------	-----------------------------

Based on the study desaturation sequence profile it is required secondary to the minimum number of subjects, that a minimum number of paired measurements for each study endpoint and capnic state will be collected as defined in Table 2.

[REDACTED]	[REDACTED]	[REDACTED]	[REDACTED]
[REDACTED]	[REDACTED]	[REDACTED]	[REDACTED]
[REDACTED]	[REDACTED]	[REDACTED]	[REDACTED]
[REDACTED]	[REDACTED]	[REDACTED]	[REDACTED]
[REDACTED]	[REDACTED]	[REDACTED]	[REDACTED]
[REDACTED]	[REDACTED]	[REDACTED]	[REDACTED]
[REDACTED]	[REDACTED]	[REDACTED]	[REDACTED]
[REDACTED]			

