14.1 Sample Size Justification

The subject population will include up to a total of 50 subjects. The planned sample size was determined through a power-based analysis based on previously collected Jugular Bulb study data during the device development cycle, and will be documented in the Statistical Analysis Plan (SAP). The study size is pre-defined to enroll up to 50 subjects accounting for larger than anticipated screen failures and subject dropouts.

This document is electronically controlled. Printed copies are considered uncontrolled.

Confidential MDT16010MAVJB3	
---------------------------------------	---

A priori statistical power analysis determined that a minimum of [REDACTED] subjects for normocapnia [REDACTED] [REDACTED] study procedures is required to achieve at least [REDACTED] power at [REDACTED] to detect a difference to [REDACTED] A_{RMS} success criterion for cerebral overall accuracy, and [REDACTED] A_{RMS} for cerebral and somatic trending accuracy. The null hypothesis and expected accuracy were adjusted conservatively, and the sample size was increased to account for any unexpected inter and intra subject variability and performance of the final revision of the INVOS system.

Based on the study desaturation sequence profile it is required secondary to the minimum number of subjects, that a minimum number of paired blood draws for each study endpoint will be collected as defined below:

[REDACTED]	[REDACTED]	[REDACTED]	[REDACTED]
[REDACTED]	[REDACTED]	[REDACTED]	[REDACTED]
[REDACTED]	[REDACTED]	[REDACTED]	[REDACTED]
[REDACTED]	[REDACTED]	[REDACTED]	[REDACTED]
[REDACTED]	[REDACTED]	[REDACTED]	[REDACTED]
[REDACTED]	[REDACTED]	[REDACTED]	[REDACTED]
[REDACTED]	[REDACTED]	[REDACTED]	[REDACTED]
[REDACTED]	[REDACTED]	[REDACTED]	[REDACTED]

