## **7.5. Adjustments for Multiple Comparisons**

No adjustments for multiple comparisons will be made.

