## **7.8. Evaluation of Objectives**

The next generation [REDACTED] system measures hemoglobin under the Sensor, allowing determining absolute levels of blood oxygenation saturation in the tissue (StO2). The INVOS algorithm determines the StO2 values for the tissue under the sensor. The next generation INVOS system will be validated over a clinical range of arterial oxygen saturations (e.g. pulse oximeter) of 70 - 100% in healthy volunteers. Next generation INVOS regional saturation (rSO2) performance will be compared to the calculated global field saturation (fSO2) value obtained from simultaneous arterial and jugular venous blood samples for the cerebral site and it will be compared to legacy INVOS rSO2 on the somatic site. Human volunteers will undergo oxygen desaturation in order to test the system over a clinical range of arterial oxygen saturation levels of 70 - 100%.

The cerebral tissue saturation can be estimated using the saturation of arterial blood (SaO2) and jugular bulb venous saturation (SjvO2).

This document is electronically controlled. Printed copies are considered uncontrolled.

Confidential MDT16010MAVJB3	[REDACTED]	[REDACTED]
---------------------------------------	------------	------------

Co-oximetry is used to determine the  $SjvO_2$  and  $SaO_2$  values ( $SaO_2$  value is taken as the average of the 2 arterial blood samples). The arteriovenous ( $fsO_2$ ) saturation is calculated as a 75:25 ratio of venous to arterial blood.

$$fsO_2 = (0.75 \times SjvO_2) + (0.25 \times SaO_2).$$

Global field saturation,  $fsO_2$  is calculated as approximation of the cerebral oxygen saturation and is used as the reference value for assessing accuracy for cerebral.

[figure not shown]
Overall accuracy will be evaluated:

At the cerebral site, by comparing next generation INVOS  $rSO_2$  with blood  $fSO_2$  values.

[figure not shown]

Trending accuracy will be evaluated:

At the cerebral site, by comparing the next generation INVOS  $rSO_2$  with blood  $fSO_2$  values.

[figure not shown]

At the somatic site, by comparing next generation INVOS  $rSO_2$  with legacy INVOS  $rSO_2$  values.

This document is electronically controlled. Printed copies are considered uncontrolled.

Confidential MDT16010MAVJB3		
---------------------------------------	--	---

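### Is 25 subjects too few because SAP section 6 sizes each of the three primary requirements on its own?

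*SAP*

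**What the plan says.** SAP section 4 gives one primary objective with three parts, namely that the system and sensors "meet product requirements for cerebral accuracy, cerebral trending accuracy, and somatic trending". Protocol 6.1.1 has the same objective.

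SAP section 6 has one paragraph for each part. Each begins "Based on data from similar studies, a mean value of [REDACTED] is assumed for" A_RMS, adds an assumed SD, and ends with the sentence "A total of 25 subjects will provide sufficient data information [Table 2] to assess the statistical hypothesis" and the statement that "power and an alpha of [REDACTED] are assumed in the estimation". It then points to Table 2 for minimum numbers of paired measurements; the contents of that table are redacted.

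Protocol 14.1 has a single power sentence. It gives a redacted minimum number of subjects and a redacted power, worded as a floor, against one A_RMS "success criterion for cerebral overall accuracy, and" a second A_RMS value shared by cerebral and somatic trending. Two criterion values thus cover three endpoints. The next sentence says that the null hypothesis and expected accuracy were set conservatively and the number of subjects raised, to allow for unexpected variability and for the performance of the final system. On the ceiling, 14.1 says "The study size is pre-defined to enroll up to 50 subjects accounting for larger than anticipated screen failures and subject dropouts".

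SAP 7.5 says "No adjustments for multiple comparisons will be made".

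**The concern.** An objective that joins three requirements reads most naturally as all three having to pass. Power for that event is lower than power for any one part, unless passing the hardest part guarantees the other two. That guarantee is unlikely here. Both cerebral endpoints are judged against blood-derived field saturation, while the somatic endpoint is judged against the legacy device: "At the somatic site, by comparing next generation INVOS" rSO2 with legacy rSO2. Yet SAP section 6 has no step that combines the endpoints, and a reader could take the single power sentence in Protocol 14.1 as the power for the whole objective.

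At stake is a failed validation of a device that works, after healthy volunteers have had jugular bulb and arterial catheters placed with no medical benefit to themselves. The chance of wrongly passing the device does not rise: under an all-must-pass rule, leaving alpha unadjusted is correct and the cost falls on power.

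**Working it through.** **1. The plan's own figure.** The 25 cannot be reproduced. The expected A_RMS, its SD, the criterion, alpha and power are redacted for every endpoint, and so are the contents of Table 2. Everything below is conditional on assumed values.

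**2. What holds without the redacted values.** Let p be the power for each endpoint. The probability of passing all three lies between 1 − 3(1 − p) and p.

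| p per endpoint | lower limit | upper limit |
|---|---|---|
| 80% | 1 − 3(0.20) = 40% | 80% |
| 90% | 1 − 3(0.10) = 70% | 90% |
| 95% | 1 − 3(0.05) = 85% | 95% |
| 99% | 1 − 3(0.01) = 97% | 99% |

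The possible loss is large at p = 80% and negligible at p = 99%. The documents do not show where 25 subjects sits on this scale.

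**3. Illustration with assumed power.** Assume a one-sample t test on per-subject A_RMS, one-sided alpha 0.05, and a standardised margin that gives exactly p at n = 25. The margin is 0.512 for p = 80% and 0.603 for p = 90%. Joint power is the trivariate normal probability that all three statistics fall below z(p). The last two columns raise n, or p, until joint power equals the assumed p.

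| p at n = 25 | cerebral–cerebral correlation | somatic–cerebral correlation | joint power | n for joint power = p | p needed at n = 25 |
|---|---|---|---|---|---|
| 80% | 0 | 0 | 0.80³ = 51.2% | 39 | 0.80^(1/3) = 92.8% |
| 80% | 0.9 | 0 | 60.0% | 36 | 90.9% |
| 80% | 0.7 | 0.7 | 65.9% | 34 | 89.4% |
| 90% | 0 | 0 | 0.90³ = 72.9% | 35 | 0.90^(1/3) = 96.5% |
| 90% | 0.9 | 0 | 78.2% | 33 | 95.7% |
| 90% | 0.7 | 0.7 | 81.0% | 32 | 95.1% |

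Using one-sided alpha 0.025 lowers these subject counts by 1 or 2. A normal approximation with a common correlation of 0, 0.5 or 0.8 gives a similar picture: joint power 51%, 61% or 69% from 80% each, and 73%, 78% or 83% from 90% each.

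**4. Which row applies.** Every row assumes that 25 gives each endpoint exactly the nominal power. The visible text points away from that. Protocol 14.1 words the power as a floor and says the number of subjects was raised on top of conservative inputs. Three calculations, each stating its own mean and SD, all end at 25, which suggests a common, rounded or largest value. If so, at least one endpoint would have more than nominal power. Suppose the hardest endpoint has 80% or 90% and the other two have 95%. With somatic independent and a cerebral correlation of 0 to 0.9, joint power is then 72–76% or 81–85%.

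**5. Limits of the model.** SAP 7.8 evaluates the primary endpoint as A_RMS pooled over subjects, so a test on per-subject values is only a stand-in. The limits in step 2 do not depend on it; the subject counts in step 3 do.

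**The case for a change.** The strongest case for a change is that the gap can be read without any redacted number. The objective has three parts, the sizing is done part by part, and no visible sentence joins them. A joint probability cannot exceed its smallest component, and the different site and reference for somatic trending make near-equality implausible. Protocol 14.1 gives variability and final-system performance as the reasons for the extra subjects, not joint success. Checking would cost little if subject-level data from the earlier studies could be resampled with all three criteria applied at once.

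The structural observation stands: joint power is not visibly stated. The step from there to 25 being too few does not.

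- The inequality applies to every study with several endpoints. It gives no size for the loss.
- Weak correlation with the somatic endpoint is assumed. The same subjects, investigational system and desaturation sequences produce all three results.
- The two documents do not conflict. A power worded as a floor can mean the minimum over endpoints, which is what three separate calculations supply.
- The all-must-pass rule is an inference from the wording of the objective. Text after Protocol 6.1.1 is redacted, and a success rule may sit there. If three stand-alone claims are intended, power per endpoint is the right quantity.
- The resampling may not be possible. The protocol synopsis says two earlier jugular bulb studies were bootstrapped by subject, but nothing visible shows that they held paired investigational and legacy somatic readings.
- The ceiling of 50 counts enrolled subjects and is reserved for screen failures and dropouts, with no rate given. It is not spare capacity for joint power. Equally, no visible rule stops enrolment at 25.

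**Conclusion.** No change follows. A deficit at 25 can be neither confirmed nor excluded from the public text. Over the correlations tabulated, it would run from about 14 to 29 percentage points if each endpoint had exactly 80% power (80 − 65.9 to 80 − 51.2), and from about 9 to 17 points at exactly 90% (90 − 81.0 to 90 − 72.9). It would vanish against an 80% target if each endpoint had about 89% to 93% power, and against a 90% target at about 95% to 97%. These figures rest on the assumed t model, one-sided alpha 0.05, equal power across endpoints and the tabulated correlations.

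No stated figure has been shown to be missed, so raising the minimum would amount to enrolling more people in an invasive study on assumed inputs. Printing a joint power or spelling out the pass rule would add detail but would not alter any estimate, test or criterion. Any risk falls on the sponsor, as a lower chance of validating a working device, and not on those who rely on a pass. The choice between one joint claim and three separate ones also belongs to the sponsor.

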## 7. Statistical Methods

### 7.1. Study Subjects

#### 7.1.1. Disposition of Subjects

Subject disposition (e.g., number completed the study, discontinued along with primary reason for discontinuation, lost-to-follow-up) will be summarized with frequency counts and the corresponding percentages.

#### 7.1.2. Clinical Investigation Plan (CIP) Deviations

The number of subjects with major protocol deviations (e.g. informed consent process or procedures are not followed, violation to inclusion or exclusion criteria, or issues with study data collection) will be summarized with frequencies and percentages.

#### 7.1.3. Analysis Sets

Subjects will be considered enrolled in the study once it has been confirmed that they meet all the inclusion and none of exclusion criteria. Unless otherwise specified, analysis of reported outcomes will include all available data for all subjects enrolled.

This document is electronically controlled. Printed copies are considered uncontrolled.

Confidential MDT16010MAVJB3	[REDACTED]	[REDACTED]
--------------------------------	------------	------------

## **7.2. General Methodology**

All statistical analyses will be performed using SAS® Version 9.3 or higher, JMP Version 11.2.0, Minitab Version 17.1.0, Matlab Version 2015a or higher, or other validated software. In general, descriptive statistics will be used to summarize the baseline and study outcomes. The statistics for continuous variables may include the number of observations (N), mean, standard deviation, median, minimum, and maximum. Categorical variables are presented using frequencies and percentages.

## **7.3. Center Pooling**

Center Pooling not applicable as this is a single center study.

## **7.4. Handling of Missing Data and Dropouts**

No imputation or other adjustment techniques are planned for the missing data to be included in the analyses.

## **7.5. Adjustments for Multiple Comparisons**

No adjustments for multiple comparisons will be made.

## **7.6. Demographic and Other Baseline Characteristics**

The baseline characteristics, including age, gender, race, ethnicity, skin tone and BMI will be summarized by using descriptive statistics.

## **7.7. Interim Analyses**

There are no requirements for an interim analysis.

## **7.8. Evaluation of Objectives**

The next generation [REDACTED] system measures hemoglobin under the Sensor, allowing determining absolute levels of blood oxygenation saturation in the tissue (StO2). The INVOS algorithm determines the StO2 values for the tissue under the sensor. The next generation INVOS system will be validated over a clinical range of arterial oxygen saturations (e.g. pulse oximeter) of 70 - 100% in healthy volunteers. Next generation INVOS regional saturation (rSO2) performance will be compared to the calculated global field saturation (fSO2) value obtained from simultaneous arterial and jugular venous blood samples for the cerebral site and it will be compared to legacy INVOS rSO2 on the somatic site. Human volunteers will undergo oxygen desaturation in order to test the system over a clinical range of arterial oxygen saturation levels of 70 - 100%.

The cerebral tissue saturation can be estimated using the saturation of arterial blood (SaO2) and jugular bulb venous saturation (SjvO2).

This document is electronically controlled. Printed copies are considered uncontrolled.

Confidential MDT16010MAVJB3	[REDACTED]	[REDACTED]
---------------------------------------	------------	------------

Co-oximetry is used to determine the  $SjvO_2$  and  $SaO_2$  values ( $SaO_2$  value is taken as the average of the 2 arterial blood samples). The arteriovenous ( $fsO_2$ ) saturation is calculated as a 75:25 ratio of venous to arterial blood.

$$fsO_2 = (0.75 \times SjvO_2) + (0.25 \times SaO_2).$$

Global field saturation,  $fsO_2$  is calculated as approximation of the cerebral oxygen saturation and is used as the reference value for assessing accuracy for cerebral.

[figure not shown]
Overall accuracy will be evaluated:

At the cerebral site, by comparing next generation INVOS  $rSO_2$  with blood  $fSO_2$  values.

[figure not shown]

Trending accuracy will be evaluated:

At the cerebral site, by comparing the next generation INVOS  $rSO_2$  with blood  $fSO_2$  values.

[figure not shown]

At the somatic site, by comparing next generation INVOS  $rSO_2$  with legacy INVOS  $rSO_2$  values.

This document is electronically controlled. Printed copies are considered uncontrolled.

Confidential MDT16010MAVJB3		
---------------------------------------	--	---

Arithmetic Root Mean Square (ARMS), standard deviation of the error and mean bias will be calculated as defined in the equations below. The primary endpoint will be evaluated to calculate pooled subject ARMS. The equations below represent calculations for overall accuracy with the error component of each equation being replaced with the error as defined in Figure 2 for trending accuracy.

$$Arms = \sqrt{\sum_{i=1}^n \frac{((rSO_2)_i - (fSO_2)_i)^2}{n}}$$

$$Std\ Dev = \sqrt{\sum_{i=1}^n \frac{((rSO_2)_i - (fSO_2)_i - Bias)^2}{n - 1}}$$

$$Bias = \sum_{i=1}^n \frac{((rSO_2)_i - (fSO_2)_i)}{n}$$

This document is electronically controlled. Printed copies are considered uncontrolled.

Confidential MDT16010MAVJB3		
---------------------------------------	--	--

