- Each desaturation sequence step will last approximately 2 to 6 minutes. All three Desaturation Sequences are presented in Figure 3 below:
 - Sequence #1: steps # 1-8
 - Sequence #2: steps # 9-13
 - Sequence #3: steps # 14-18 [REDACTED]
- The first two desaturation sequences are conducted in subject specific normocapnia and the third desaturation sequence will be conducted under [REDACTED].
 - [REDACTED]
 - [REDACTED]
 - [REDACTED]
 - [REDACTED]
- Modifications to the hypoxia sequence for patient safety will be left to the judgment of the Principal Investigator.

This document is electronically controlled. Printed copies are considered uncontrolled.

Confidential MDT16010MAVJB3	[REDACTED]	[REDACTED]	[REDACTED]
---------------------------------------	------------	------------	------------

- Study Blood Draws:

[figure not shown]
- At each plateau, after ~ █ minutes wait time (stability period) and extended wait time ~ █ minutes for return to room air and 100% oxygen saturation steps, two paired (simultaneously drawn) jugular bulb vein and arterial blood samples are drawn (█). Draw waste or leader blood samples prior to the draw of paired blood samples may be used to ensure the accuracy of blood samples.
- Co-oximetry is used to determine the jugular venous saturation ($SjvO_2$) and arterial saturation (SaO_2). Each blood sample will be analyzed multiple times or using multiple co-oximeter machines. Blood samples will be averaged to provide one $SjvO_2$ and one SaO_2 value for each paired draw at that plateau. Blood samples are analyzed in real-time and results from the co-oximeters will be stored electronically.
- Co-oximetry raw data (co-oximeter blood oximetry results and the time of analysis) will be provided to Medtronic. █
█
█
█
- The jugular sample will be drawn approximately over a period of █ (targeting rate of █).
○ The arterial sample will be drawn at approximately the midpoint of the jugular bulb draw.
○ Each blood draw (either venous or arterial) is approximately 1.5 ml, totaling approximately █ ml per paired sample (pair = 1 jugular plus 1 arterial).
○ With a target of two paired samples per plateau step, a total of █ paired arterial and venous draws may be collected during the study. Total blood draw during the study is estimated to be █. If less than the targeted █ pairs of blood samples are collected, it will not be considered a protocol deviation.

After the procedure:

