**Capnic State Analysis:**

The pCO2 will be averaged for the two arterial blood draws taken at each oxydenation plateau and multiple COOX measurements evaluating the samples.

pCO2 measured by blood draw co-ocimeter analysis will be analyzed per subject for normocapnic [REDACTED] states independently by mean, median, standard deviation, min, max.

Additional statistical analyses may be performed for supporting evidence in meeting study endpoints.

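### Does the two-sample averaging of SaO2 in SAP 7.8 undermine an fSO2 reference built per paired draw?

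*SAP*

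**What the plan says.** SAP 7.8 gives fSO2 as 0.75 × SjvO2 + 0.25 × SaO2. It adds in parentheses that the SaO2 "value is taken as the average of the 2 arterial blood samples". For SjvO2 it says only that co-oximetry determines it. The same section describes fSO2 as a "value obtained from simultaneous arterial and jugular venous blood samples".

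Other places work by the paired draw:

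- Protocol 10.5.1 defines a pair as one jugular plus one arterial sample and targets two pairs per plateau. Each sample is analysed several times or on several machines. The results are averaged to one SjvO2 and one SaO2 "value for each paired draw at that plateau". On timing: "The arterial sample will be drawn at approximately the midpoint of the jugular bulb draw".
- SAP 5 lists "2 blood draws and monitor measurements at each oxygenation plateau". It says that an fSO2 "is created for each paired blood draw" and compares it with rSO2 averaged over the time span of that draw.
- Protocol 14.1 requires that "a minimum number of paired blood draws for each study endpoint will be collected".

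The Capnic State Analysis text in the SAP says that pCO2 "will be averaged for the two arterial blood draws taken at each oxydenation plateau and multiple COOX measurements evaluating the samples".

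**The concern.** A pair holds only one arterial sample, so two arterial samples suggests both draws of a plateau. The pCO2 text supports this, because it names the two arterial draws separately from the repeat co-oximeter measurements. Applied literally, the SAP 7.8 sentence would combine a plateau-mean SaO2 with an SjvO2 and an rSO2 that belong to a single draw. The three quantities would then not be simultaneous.

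fSO2 is the reference for cerebral overall and cerebral trending accuracy. It enters A_RMS, bias and the standard deviation of errors, as well as the regression, Bland-Altman, random-coefficients and concordance analyses. Two programmers could in principle compute different reference values from the same blood results.

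**Working it through.** **Reading the passages together.** Protocol 10.5.1 first says that each sample is analysed repeatedly, and then that samples are averaged to one SaO2 per paired draw. Since a pair contains one arterial sample, the Protocol is using the word samples for repeat readings of one sample. SAP 7.8 may use the same shorthand, and on that reading nothing conflicts. The pCO2 text points both ways: it separates draws from readings, but it also shows that the SAP names the plateau when it means plateau averaging. The SAP 7.8 parenthesis does not name it.

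**Size if the sentence is taken literally.** No figure in the plan depends on this point, so there is none to reproduce. Inputs:

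- Weight on SaO2: 0.25 (SAP 7.8).
- SaO2 difference between the two draws of a plateau, D: not given; assumed to be 2 or 4 points.
- A_RMS under the per-pair rule, A: the expected value is redacted; assumed to be 3, 4 or 6.

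Each draw lies D/2 from the two-draw mean, so each fSO2 shifts by s = ±0.25 × D/2 = ±D/8. That is 0.25 point at D = 2 and 0.5 point at D = 4. With both draws present, the two shifts cancel in the mean bias for overall accuracy.

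The effect on A_RMS depends on why the draws differ:

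- *Real drift that rSO2 follows.* The shift is uncorrelated with device error, so A' = √(A² + s²).
- *Sampling or analyser noise on a stable plateau.* The per-pair error already contains that noise, and averaging removes part of it, so A' = √(A² − s²).

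| D | A | Drift: A' | Noise: A' |
|---|---|---|---|
| 4 | 3.00 | √9.25 = 3.04 (+1.4%) | √8.75 = 2.96 (−1.4%) |
| 4 | 4.00 | √16.25 = 4.03 (+0.8%) | √15.75 = 3.97 (−0.8%) |
| 4 | 6.00 | √36.25 = 6.02 (+0.3%) | √35.75 = 5.98 (−0.3%) |
| 2 | 4.00 | √16.0625 = 4.01 (+0.2%) | √15.9375 = 3.99 (−0.2%) |

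A simulation of 25 subjects, 18 plateaus and two draws agreed with the drift formula to within sampling error. It builds in the drift assumption, so it checks the algebra and not the direction.

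**Trending.** The figure that defines the trending error is not shown. Suppose the error is taken on change from the first data point of a sequence. The baseline then carries its own shift. If its sign is unrelated to that of the later point, the added mean square is 2s². At D = 4 this is 0.5, and in the drift case A = 4.00 becomes √16.5 = 4.06 (+1.6%).

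**The case for a change.** The best case for a change is that SAP 7.8 is where the reference value is defined, and such a definition should have one reading before analysis. The sentence also has no literal meaning when a plateau yields only one arterial sample. Protocol 10.5.1 allows that without a deviation, and SAP 7.4 plans no imputation. Finally, a programmer might fill the silence on SjvO2 by averaging it too. If SjvO2 moved by the same D, the shift would be D/2. At D = 2, A = 4.00 would become √(16 + 1) = 4.12, and 18 completed steps would give 18 distinct reference values per subject instead of 18 × 2 = 36.

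The wording mismatch does stand; it is in the visible text. The consequences are weaker. Averaging SjvO2 has no support in the visible text and would contradict Protocol 10.5.1, which gives one SjvO2 per pair. The SAP is therefore silent where the Protocol is not. A plateau with one arterial sample raises no difficulty under the per-pair rule. Protocol 14.1 does not settle the matter either, because it counts draws to be collected and not reference values.

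The per-pair rule is also not shown to be the better reference. On a steady plateau, averaging two SaO2 values could reduce noise, so insisting on one rule would choose the sponsor's intent for it. Text beside the fSO2 statement in SAP 5 is blacked out and figures in SAP 7.8 are missing from the copy reviewed, so the full documents may already resolve the wording.

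**Conclusion.** This is ambiguous wording that an analyst would resolve sensibly, and no change to the plan follows. The rule for both SaO2 and SjvO2 is in Protocol 10.5.1, and SAP 5 builds fSO2 on the same unit.

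If the parenthesis were nevertheless applied literally to SaO2 alone, overall-accuracy A_RMS would move by about 1.4% or less, for an assumed between-draw difference of up to 4 points and an A_RMS of 3 or more. Four points at every plateau is a stress case, since samples are drawn after a stability wait. The direction is not established, so the wording cannot be said to favour the device or to penalise it. Mean bias for overall accuracy is unchanged when both draws are present, and the somatic endpoint is untouched because its comparator is the legacy device. The acceptance limits are redacted, so the margin to them cannot be checked. Nothing visible suggests that the cerebral conclusions would turn on a shift of this size.
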